## **Introduction:**

Nitrous oxide donors are widely used in clinical practice for many medical conditions. Nitrous oxide (NO) is known to have a secondary messenger role in signal transduction process for many cellular functions. NO signal transduction pathway is mediated by another secondary messenger, cGMP, through activation of guanyl cyclase which in turn participate in a cellular process. For instance, NO is produced by the endothelial cell layer of blood vessels causing relaxation of the blood vessel smooth muscles and causes vasodilation (endothelial derived relaxing factor, EDRF) (Ignarro, 1990). The same mechanism may cause relaxation of other smooth muscles in the body. In the obstetrics and gynecology field it is approved for tocolysis in cases of risk of preterm labor (Green-top guidelines, 2011).

NO is expected to have a role in the remodeling process that occur in the cervix prior to onset of labor. During the cervical ripening process, chemical and physical changes to the *collagen* composition of the cervix are required to make the cervix more soft and distensible for effacement and dilation during normal delivery (Liu et al., 2014). There is an increasing evidence that there is a rise in the activity of inducible NO synthase (iNOS)

in the cervix before the onset of labor which may have a role in the ripening process (Tschugguel et al., 1999).

Many studies have been held out to establish the efficacy of the NO donors in promoting cervical ripening and labor induction. Many patients who need termination of pregnancy may benefit its use as a safe and affordable method. Nevertheless, there is so much debate regarding their ability to have such effect. Some studies concluded that NO donors guarantee a safe method for outpatient induction of labor (Bullarbo et al., 2007). Other studies disagreed that they have any considerable action at all. They concluded that NO donors do not appear to be a useful tool in the process of induction of labor (Collingham et al., 2010).

There is an increasing rate of deliveries by caesarean section in Egypt lately (DHS, 2014). One of the major causes that makes the obstetrician favors delivery by caesarean section is fear of failure or complications of induction of labor. Many preparations used in induction of labor have been associated with fetal and maternal compromise. While in developed countries, labor induction is widely

practiced; for example it accounts for 20% of pregnancies in the UK. Therefore, the search of a safer and reliable method of induction is still ongoing (NHS Maternity statistics, 2015).

A *Cochrane* systemic review in 2011 considered 19 trial studies to compare the efficacy of NO donors in labor induction with other agents. It concluded that NO donors do not appear to be more useful than other agents. It suggested that more studies are required to examine how NO donors may work alongside established induction of labor protocols, especially those based in outpatient settings (Kelly et al., 2011).

# **Aim and Objectives:**

Aim: This study aims to establish the efficacy of nitroglycerine skin patch as a NO donor in addition to dinoprostone for induction of labor.

Objectives: The primary outcome of the study is to compare the changes occurring to the cervix through the progression in the Bishop's score between NO donor (nitroglycerine patch) vs placebo; in combination with a well-established method of induction (Dinoprostone).

The secondary objective of the study is to observe and report possible fetal and maternal side effects that may be associated. This will establish the safety and tolerability of NO donors.

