# **Methodology:**

This study will be a double-blinded randomized controlled trial and will be conducted in Ain Shams University Maternity Hospital. It will include 100 pregnant women at term who will be indicated for induction of labor.

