## Sample Size Justification:

The study was calculated using STATA® version 11 program, setting the type-1 error at 0.5 and the power  $(1-\beta)$  at 0.8. Sample size is correlated to former studies in induction of labor (Collingham et al., 2010). Calculation according to these values produced a minimal sample size of 45 cases in each group.

Alpha error= 0.05 (two sides) Power of study= 0.8

Based on favorable outcome of cervix (p1= 41%, p2=81%) with ratio of intervention group to control group 1:1.

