#### **Data presentation and Statistical Methods:**

Data will be collected, tabulated, then analyzed using PC using Statistical package for Social Science (SPSS 15.0.1 for windows; SPSS Inc, Chicago, IL, 2001).

Normally distributed numerical data will be presented as mean and SD, and skewed data as median and interquartile range. Qualitative data will be presented as number and percentage.

Comparison between the means will be done by paired t test for independent samples. Skewed data will be compared using the Mann-Whitney test. Categorical data will be compared using the chi-squared test for qualitative data comparison.

A p-value <0.05 will be considered statistically significant.

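### The safety objective says more than the design can deliver: about 50 women given one nitroglycerine patch can describe its common side effects, but cannot establish safety for uncommon harms or for NO donors as a class

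*Protocol*

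**What the plan says.** Two consecutive statements in the Protocol, Aim and Objectives, set the safety objective. The first is descriptive: "The secondary objective of the study is to observe and report possible fetal and maternal side effects that may be associated". The second states what follows from it: "This will establish the safety and tolerability of NO donors".

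The rest of the protocol fixes what the safety data will be:

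- **Size.** Methodology: "It will include 100 pregnant women at term who will be indicated for induction of labor". Sample Size Justification gives a "minimal sample size of 45 cases in each group" and allocation "with ratio of intervention group to control group 1:1". The calculation rests only on a favourable cervix, 41% against 81%.
- **Exposure.** Under Method, the only NO donor given is one nitroglycerine skin patch product, applied at admission, and both groups receive dinoprostone.
- **Population.** The exclusion criteria remove women with obstetric or medical complications and any other general or obstetric risk.
- **Outcomes.** The list of group comparisons names headache, nausea and postpartum hemorrhage for the mother, and Apgar score at 1 and 5 minutes for the newborn.
- **Criterion.** Data presentation and Statistical Methods gives one general threshold: "A p-value <0.05 will be considered statistically significant". The protocol states no event rate, margin or precision target for any safety outcome.

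**The concern.** An objective tells the reader what the trial may conclude. This one promises, before any data exist, that safety will be established, and for NO donors in general. The design falls short in two separate ways.

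**Size.** The number of exposed women was chosen for a large effect on the cervix. It leaves the rate of any uncommon harm poorly bounded, even if no such harm is seen.

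**Scope.** One transdermal product, in a selected population and on a background of dinoprostone, does not represent a drug class. The protocol's own reference list shows that the class is wider: two of the cited trials used isosorbide mononitrate.

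At stake is the wording of the eventual safety conclusion. The Introduction says that many preparations used for induction have been associated with fetal and maternal compromise, so readers will give weight to a claim of established safety.

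**Working it through.** **Inputs from the protocol.** Total 100 women (Methodology) and 1:1 allocation (Sample Size Justification), so 100/2 = 50 exposed to the active patch; stated minimum 45 per group; two-sided alpha 0.05 ("Alpha error= 0.05 (two sides) Power of study= 0.8"). **Assumed inputs.** All safety event rates below, because the protocol gives none.

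**0. The plan's own figure.** The 45 per group comes from 41% against 81% for the cervix. The standard two-proportion formula at two-sided 0.05 and power 0.8 gives 23 per group (27 with continuity correction), so the figure does not reproduce. That is a separate matter. What counts here is that no safety rate entered the calculation.

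**1. Upper limit when no event is seen (no assumed rate needed).** If no event occurs in n women, the exact upper limit solves (1 − p)^n = a, so p = 1 − a^(1/n).

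| Exposed women | One-sided 95% (a = 0.05) | Two-sided 95% (a = 0.025) |
|---|---|---|
| 50 | 1 − 0.05^(1/50) = 5.8% | 1 − 0.025^(1/50) = 7.1% |
| 45 | 1 − 0.05^(1/45) = 6.4% | 1 − 0.025^(1/45) = 7.9% |

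A completely clean record for a given harm would therefore still be compatible with a true rate of roughly 1 in 17 (one-sided) or 1 in 14 (two-sided).

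**2. Chance of seeing a harm at all.** P(at least one event in 50) = 1 − (1 − p)^50. For an assumed p = 1% this is 1 − 0.99^50 = 39.5%. A harm of that frequency would be absent from the active arm in about 60% of such trials.

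**3. Power of the chi-squared comparison.** Pearson test without continuity correction, 50 per arm, two-sided 0.05. Power is the sum of the binomial probabilities of all 51 × 51 outcome tables that the test rejects. All rates are assumed.

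| Control | Active | Power |
|---|---|---|
| 5% | 10% | 14% |
| 5% | 15% | 39% |
| 5% | 20% | 66% |
| 10% | 35% | 88% |
| 10% | 40% | 95% |

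The first three rows show what happens with uncommon harms. The last two show that a large difference in a common effect would probably be detected.

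**4. Precision of a difference.** With an assumed 5% rate in both arms, the approximate 95% half-width is 1.96 × √(2 × 0.05 × 0.95 / 50) = 8.5 percentage points, wider than the rate itself. For a single arm with an effect at 50%, it is 1.96 × √(0.5 × 0.5 / 50) = 13.9 points, which is adequate for describing a frequent side effect.

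**5. Scope.** This needs no arithmetic. The sentence refers to NO donors; the trial gives one nitroglycerine patch product. A larger trial of the same patch would narrow the intervals in steps 1 to 4 and still say nothing direct about other agents or routes.

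**The case against.** **The operative objective is already descriptive.** The sentence just before the claim commits only to observing and reporting, the hypotheses concern ripening and induction alone, and no safety hypothesis or margin appears anywhere. This stands, and it is why the point is about wording and not a fault in design or analysis. It does not rescue the claim, because observing and reporting at this size cannot amount to establishing safety. The two sentences need reconciling.

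**NO donors may be shorthand for the study patch.** The same section calls the patch an NO donor, and the research question and hypotheses name only nitroglycerine. That reading is possible and softens the scope argument. The sentence as written is nevertheless class-wide, and naming the patch removes the doubt.

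**The event rates are the reviewer's choice.** True for steps 2 to 4. The zero-event limits in step 1 need no assumed rate.

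**Tolerability can be studied here.** This stands. A reader might infer that 100 women can say nothing useful about side effects. The figures do not support that: power is 88% for an assumed 10% against 35%, so the shortfall is confined to uncommon harms and to the class.

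**A non-significant difference would be read as safety.** A reader might infer this from the promise to establish safety combined with a single p-value threshold. The protocol does not say it. The statistical section says when a result counts as significant and gives no rule for the opposite case, so this is a risk to close off and not a stated error.

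**Intervals belong in a statistical analysis plan.** Their absence from the protocol is not held against it. The point rests on a claim the protocol makes, and no analysis plan could make about 50 exposed women sufficient for uncommon harms.

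**Conclusion.** Wrong as written, minor severity. The sentence attributes to the trial a property it does not have. With about 50 exposed women, zero events of a given kind leaves an upper 95% limit of 5.8% one-sided or 7.1% two-sided (6.4% or 7.9% at the stated minimum of 45). Under an assumed rise from 5% to 15%, power is 39%. Separately, one patch product given with dinoprostone to women selected for low risk cannot stand for NO donors in general.

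The limits assume that all 50 women in the active arm receive the patch and are followed for the harm in question; losses would widen them. The power figures depend on assumed rates and on the uncorrected chi-squared test. The descriptive objective is sound and should stay.

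**What to change.** Keep the sentence on observing and reporting side effects. Replace the one that follows it with:

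> *The side effects and tolerability of the nitroglycerine patch will be described by arm, with 95% confidence intervals for the difference; the trial is not sized to establish safety, and a non-significant difference in harms will not be interpreted as evidence of safety.*

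Quoting the zero-event limit for 50 women in the objectives is optional; it could equally go in the analysis plan or the discussion of results.

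The cost is one sentence in the objectives and an interval column in the safety table. The stated claim becomes less favourable. Sample size, treatment, data collection and the primary analysis do not change.

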# **Research Question:**

Does the usage of Nitroglycerine skin patch enhance cervical ripening and facilitate induction of labor by Dinoprostone?

# **Research Hypothesis:**

*Null hypothesis*: Nitroglycerine skin patch does not cause advantage for ripening of the cervix nor facilitate the process of labor induction.

Alternative hypothesis: Nitroglycerine skin patch has favorable effect in enhancing cervical ripening and the outcome of induction of labor.

# **Methodology:**

This study will be a double-blinded randomized controlled trial and will be conducted in Ain Shams University Maternity Hospital. It will include 100 pregnant women at term who will be indicated for induction of labor.

## Sample Size Justification:

The study was calculated using STATA® version 11 program, setting the type-1 error at 0.5 and the power  $(1-\beta)$  at 0.8. Sample size is correlated to former studies in induction of labor (Collingham et al., 2010). Calculation according to these values produced a minimal sample size of 45 cases in each group.

Alpha error= 0.05 (two sides) Power of study= 0.8

Based on favorable outcome of cervix (p1= 41%, p2=81%) with ratio of intervention group to control group 1:1.

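### The sample size of 45 per group does not follow from its stated inputs, which need 23 to 27, and the same section gives the type-1 error as both 0.5 and 0.05

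*Protocol*

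**What the plan says.** The Protocol's Sample Size Justification names a Stata calculation, "setting the type-1 error at 0.5 and the power" at 0.8, and reports its result: "Calculation according to these values produced a minimal sample size of 45 cases in each group". It then lists the inputs. The error rates are "Alpha error= 0.05 (two sides) Power of study= 0.8", and the effect is "Based on favorable outcome of cervix (p1= 41%, p2=81%) with ratio of intervention group to control group 1:1". The rates are linked to an earlier induction study. No allowance for dropout is mentioned.

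Two other places bear on the point. The Methodology section plans 100 women, which is 50 per group at 1:1. The section on data presentation and statistical methods fixes the test level: "A p-value <0.05 will be considered statistically significant".

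**The concern.** The section supplies everything a two-proportion calculation needs and presents 45 as its direct output, so the figure can be checked. A 40-point difference is very large, and 45 per group is far more than such a difference normally requires at 80% power. At least one of the two rates, the power and the sample size therefore appears to be wrong. Separately, two values of alpha a factor of ten apart stand in one short section, and only one can be right.

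What is at stake is whether a reader can tell which effect the trial was designed to detect. A 40-point difference with very high power and a difference of about 30 points with 80% power are different designs, and the text is compatible with either. A result that is not significant could not be set against a known design effect. An ethics committee could not judge whether the number of women enrolled is the number needed.

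**Working it through.** **Inputs (Protocol, Sample Size Justification).** p1 = 0.41, p2 = 0.81, ratio 1:1, two-sided alpha 0.05 (z = 1.960), power 0.8 (z = 0.842). Stated result: 45 per group.

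**Attempt to reproduce 45.** Pooled formula:

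n = [z(1−α/2)·√(2p̄(1−p̄)) + z(power)·√(p1(1−p1) + p2(1−p2))]² / (p2 − p1)²

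- p̄ = (0.41 + 0.81)/2 = 0.61, and 2 × 0.61 × 0.39 = 0.4758, with root 0.690
- 0.41 × 0.59 + 0.81 × 0.19 = 0.2419 + 0.1539 = 0.3958, with root 0.629
- n = (1.960 × 0.690 + 0.842 × 0.629)² / 0.16 = 22.1, so **23 per group**

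With the continuity correction:

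n′ = (n/4)·[1 + √(1 + 4/(n·|p2 − p1|))]² = (22.12/4)·[1 + √(1 + 4/(22.12 × 0.40))]² = 26.9, so **27 per group**

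**Other versions with the same rates:**

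| Version | n per group |
|---|---|
| Unpooled variance | 19.4, so 20 |
| Arcsine | 21.7, so 22 |
| Fisher's exact test, smallest n with power of at least 0.80 | 26 |
| One-sided 0.05 | 18 (corrected 23) |
| Two-sided alpha 0.5 | 6.2, so 7 (corrected 10.6, so 11) |
| Power 0.90 | 30 (corrected 34) |
| Power 0.95 | 36 (corrected 41) |

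None gives 45. The ratio of stated to required is 45/27 = 1.7 or 45/23 = 2.0. Reaching 45 from 27 by dropout inflation would need 1 − 27/45 = 40% dropout, and none is stated.

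**Power that the stated rates imply.** Normal approximation:

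power = Φ{[0.40·√n − 1.960 × 0.690] / 0.629}

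| n per group | Normal approximation | Exact binomial, uncorrected chi-squared | Exact binomial, corrected chi-squared |
|---|---|---|---|
| 45 | 0.983 | 0.982 | 0.967 |
| 50 | 0.991 | 0.990 | 0.983 |

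The plan states 0.8.

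**Difference that the stated size and power imply.** Solving the formula for p2 from a 41% base at 80% power gives:

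- 45 per group: 70.0% (corrected 72.1%), a difference of 29 to 31 points
- 50 per group: 68.6% (corrected 70.5%), a difference of 28 to 30 points

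**Possible sources of 45.** Each fits, and the document confirms none.

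- 51% vs 81% with continuity correction gives 44.4, so 45. This would be a mistyped p1.
- 41% vs 70% without correction gives 44.9, so 45.
- The uncorrected total for the stated inputs is 2 × 23 = 46, close to 45, so a total may have been reported as a per-group number.

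**The case against.** The strongest reply is that the error runs in the safe direction. Both the stated minimum of 45 and the planned 50 per group exceed what 41% vs 81% needs, so no test, threshold or enrolment figure has to change. That is correct. The point is not that the trial is too small for its stated effect. But the reply assumes that the rates are right and the sample size is the slip, and the document does not settle that. If a rate is the slip, the trial was sized for a smaller difference and has no such surplus.

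The alpha of 0.5 can fairly be called a misprint, since the same section restates 0.05 and the analysis section tests at 0.05. This stands: it needs a one-figure correction and does not weigh much alone.

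It is also fair that a null result is read mainly from the estimate and its confidence interval, which do not depend on the planning rates. What is lost is the link between the result and the effect the trial was planned to find.

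Lastly, power of 98 to 99% refers to the binary favourable-cervix outcome, whereas the primary outcome is progression of the Bishop score. The binary outcome is the Protocol's own basis for sizing, so the check is a proper one, but any restated power must be labelled as belonging to that outcome. Likewise, 51% vs 81% is only one candidate explanation and should not be adopted without the sponsor's confirmation.

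**Conclusion.** The concern holds, and the text must be corrected. At the stated alpha and power, the stated rates require 23 to 27 women per group by the usual formulas (20 to 27 across all two-sided versions tried), not 45. Choice of formula and rounding cannot account for a gap of 1.7 to 2.0 times. Separately, one of the two alpha values is certainly wrong. The evidence points to 0.5, and that slip does not explain 45.

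The conclusion rests on taking the listed inputs as those used, as the section says, with no unstated inflation. The 50 per group assumes that the 100 women are split 1:1. Which of the rates, power or sample size is at fault cannot be determined from the document.

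**What to change.** 1. Change the type-1 error of 0.5 to 0.05.
2. Go back to the calculation that was run and make inputs and result agree, leaving enrolment unchanged. Do one of the following:
   - (a) Replace p1 and p2 with the rates actually used, and name the formula. 51% vs 81% with continuity correction would reproduce 45, but the sponsor must confirm the rates.
   - (b) Keep 41% vs 81%, withdraw the claim that 45 is the minimum for 80% power, and give the power as about 98% at 45 and 99% at 50 per group, stated to be for the binary favourable-cervix outcome.
3. Add the difference that the planned 50 per group detects with 80% power: 41% vs about 69 to 70%.

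The cost is one rewritten paragraph and no extra patients. The justification will look less tidy, because it will show either a smaller design effect or a trial larger than 80% power requires.

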# Both groups will be compared regarding:

- Time from the start of labor induction to vaginal delivery
- > Time from start of drug administration to the earliest uterine contraction
- ➤ Progression of Bishop's score
- ➤ Duration of the first, second and third stages of labor
- ➤ Whether they eventually need to have a cesarean section or not.
- ➤ Incidence of maternal complications, namely; headache, nausea, postpartum hemorrhage,
- > Neonatal outcome through Apgar score at 1 and 5 minutes after delivery.

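### The 80% power is stated for a favorable-cervix proportion that the protocol never declares as an outcome, so it does not describe the Bishop score primary outcome, and it does not fit that proportion either

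*Protocol*

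**What the plan says.** The Sample Size Justification gives "Alpha error= 0.05 (two sides" sides and "Power of study= 0.8", and then the effect: "Based on favorable outcome of cervix (p1= 41%, p2=81%) with ratio of intervention group to control group 1:1". It reports a minimum of 45 per group. The Methodology section plans 100 women, which is 50 per group at 1:1.

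The Aim and Objectives section states the primary outcome differently. It is to "compare the changes occurring to the cervix through the progression" in the Bishop score. Evaluation of the effect again refers to changes and progression of the score, assessed at the second dose and at 12 and 24 hours, and names none of these as primary. The list headed "Both groups will be compared regarding" includes progression of the Bishop score but no favorable-cervix proportion.

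The nearest thing to a definition of favorable is in the Assessment section, under the Bishop table: 5 or less is unfavorable and 6 or higher is ripe. It is given there as clinical background, not as an endpoint. No mean change or SD for the score appears anywhere in the protocol.

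**The concern.** A power statement means something only for a defined outcome, at a defined time, with a stated effect. Here the effect belongs to a proportion with no cut-off and no time point, while the primary outcome is progression of a score for which no effect or SD is given. The two are related, but they are different quantities with different power.

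The protocol therefore does not tell a reader what difference in Bishop score progression the trial was built to find. If the primary comparison is not significant, the 80% cannot be used to say which differences the trial was likely to have detected. The confidence interval would still be informative, so the result is not uninterpretable, but the planned sensitivity is unknown.

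**Working it through.** **Inputs.** From the Sample Size Justification: two-sided alpha 0.05, power 0.80, p1 = 0.41, p2 = 0.81, ratio 1:1, 45 per group. From Methodology: 50 per group. The same paragraph also has "setting the type-1 error at 0.5 and the power"; that conflict is a separate matter, and 0.05 is used here because the data presentation section also sets significance at p < 0.05. Normal quantiles are 1.960 and 0.842. SDs for the score are assumptions.

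**1. The plan's own figure.** For two proportions with pooled variance under the null,

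n = [1.960·√(2·p̄(1−p̄)) + 0.842·√(p1(1−p1) + p2(1−p2))]² / (p2−p1)²

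- p̄ = (0.41 + 0.81)/2 = 0.61, and √(2·0.61·0.39) = 0.690
- √(0.41·0.59 + 0.81·0.19) = √0.3958 = 0.629
- n = (1.352 + 0.529)² / 0.40² = 3.54/0.16 = 22.1, so 23 per arm

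The other usual variants are close: 27 with continuity correction, 20 with unpooled variance, 22 by arcsine. None gives 45 at the stated alpha and power. To reach 45 by allowing for loss would take 1 − 27/45 = 40% loss from the corrected figure, or 1 − 23/45 = 49% from the uncorrected one, and the protocol states no loss rate.

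**2. Power for the binary effect at the planned size.** z = (0.40·√n − 1.352)/0.629.

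- n = 45: (2.683 − 1.352)/0.629 = 2.12, power 98.3% (97.0% by Fisher's exact test)
- n = 50: (2.828 − 1.352)/0.629 = 2.35, power 99.1%

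**3. Where 80% falls on the binary scale.** Holding 41% fixed, the same formula gives 80% power for 41% versus 70% at 45 per arm, and for 41% versus 68.6% at 50 per arm. For 41% versus 60% at 45 per arm, power is 44%.

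**4. What the same size gives for a score change.** By normal approximation, the detectable difference in SD units is d = (1.960 + 0.842)·√(2/n).

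- n = 45: 2.802·√(2/45) = 0.59
- n = 50: 2.802·√(2/50) = 0.56

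With the t distribution these become 0.597 and 0.566. In points, using the t-based values:

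| Assumed SD (points) | 45 per arm | 50 per arm |
|---|---|---|
| 1.5 | 0.9 | 0.85 |
| 2.0 | 1.2 | 1.1 |
| 2.5 | 1.5 | 1.4 |

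If the true difference were 1 point (also an assumption), power at 45 per arm by normal approximation would be about 88%, 66% and 48% for these three SDs. The protocol gives nothing with which to choose among them.

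**The case against.** The best defence is that favorable simply means a Bishop score of 6 or higher, tested by chi-squared, and that this falls under progression of the score. The text is compatible with that. The data presentation section assigns tests by type of data and never names the Bishop score, so it does not commit the primary outcome to a t test or Mann-Whitney test. A reader might infer that the binary analysis will not be run; the document supports only that the protocol does not define it. The defence still fails as a justification of the 80%. No cut-off is declared for an endpoint, none of the three assessments is tied to 41% versus 81%, and under this reading the power at 45 per arm is about 98%.

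A reader might also infer that the trial is too small. Nothing shows this: 0.57 to 0.60 SD may or may not be adequate, and that depends on an SD and a worthwhile difference that the protocol does not give.

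Finally, it is tempting to set 41% versus 81% against the Introduction's summary of the trial cited in the sample-size section ("They concluded that NO donors do not appear to be a useful tool in the process of induction of labor"). The sample-size section says only that the size relates to earlier induction studies. It does not say that the two rates come from that trial, and a one-line conclusion does not show what cervical rates it reported. No weight is put on this.

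It is fair to object that restating a detectable difference for a fixed number of women describes the trial rather than justifies its size. That stands. The restatement shows what the trial can find; whether the difference matters clinically is for the investigators to argue.

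**Conclusion.** The point holds. The stated 80% power is attached to an undeclared proportion and does not describe the stated primary outcome. It is also not the power for that proportion: the stated inputs need about 23 per arm (27 with continuity correction), and 45 per arm gives about 98%. These binary-scale results use only the protocol's own figures, with alpha taken as 0.05. The score-scale results (0.60 SD at 45 per arm, 0.57 SD at 50) assume a two-sample t comparison of score change at one time point; their values in points rest on assumed SDs. The finding concerns what the power statement describes. It is not a finding that the trial is underpowered. It should be corrected, since it bears on how the primary result is read.

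**What to change.** Keep 100 women.

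1. In Evaluation of the effect, name one of the listed assessments as the primary time point.
2. In the Sample Size Justification, state that 45 evaluable women per arm (50 enrolled) give 80% power at two-sided 0.05 for a difference of about 0.60 SD in Bishop score change at that time (0.57 SD at 50 per arm). Give the SD in points as an assumption; for example, 0.9, 1.2 or 1.5 points for an SD of 1.5, 2.0 or 2.5.
3. Settle the role of the proportion. Either list favorable cervix (score 6 or higher, as in the Assessment section) at the same time point as a secondary outcome tested by chi-squared, or, if it was meant to be primary, declare it in Aim and Objectives with its cut-off and time point. In the second case it replaces the score-based statement in step 2, and the power becomes about 98% for 41% versus 81% at 45 per arm, or the detectable difference becomes 41% versus 70% at 80% power.

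The cost is one design decision (the primary time point), a rewritten sample-size paragraph and a line in the outcome sections. No patients are added. The detectable difference becomes explicit and may look less favorable than the present wording.
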